Number of Participants:

A maximum of 16 healthy male or female participants will be enrolled. Due to the relatively small size of the study, participants who discontinue may be replaced.

Intervention Groups and Duration:**Part A - SAD**

The SAD of LY3526318 or placebo will be administered, beginning at a dose of 100 mg, the dose level that produced the highest exposure in Study CVAA. A single cohort of 8 healthy participants will be randomized to a sequence in which LY3526318 or placebo will be administered in a 3:1 ratio. In each dosing period, different participants will receive placebo. In this adaptive dose study, subsequent dose levels will be selected based on safety and PK. Doses will be selected to maintain geometric mean AUC_{0-24} below the lowest NOAEL from animal-toxicology studies (154 $\mu\text{g}\cdot\text{h}/\text{mL}$).

Following a screening period of up to 28 days, eligible participants will be confined to the clinical research unit (CRU) from Day -1 until all study assessments are completed on Day 3.

Sentinel dosing is not planned as this is not the first clinical study for LY3526318. Dose escalations to subsequent cohorts may occur at approximately 2-week intervals after review of safety data and available PK data through 24 hours post dose from at least 4 participants on active drug from the prior period. Of the 4 treatment periods planned for Part A, up to 3 single dose levels will be assessed in a fasted state (fasting at least 8 hours prior to and at least 4 hours after dosing). Up to two of these dose levels that were assessed in a fasted state may also be assessed in a fed state (a high-fat meal or a light breakfast 30 minutes prior to dosing).

Participants will return to the CRU for a final follow-up visit approximately 10 days after the final study intervention administration.

Part B - MD

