4.1. Overall Design

This is a Phase 1, SAD (Part A) and MD (Part B) study of LY3526318 in healthy participants. Both parts are randomized, double-blind, and placebo-controlled. A maximum of 16 participants (SAD and MD cohorts of size 8, randomized 3:1) will be randomly assigned to study intervention such that approximately 16 evaluable participants complete the study.

Part A (SAD):

Single-ascending doses of LY3526318 or placebo will be administered under fasted conditions, beginning with a dose of 100 mg in a cohort of 8 participants. Up to 3 dose levels in a cohort of participants will be administered in a fasted state (fasted for at least 8 hours prior to dosing and for at least 4 hours after dosing). The dose escalation may be stopped if a projected dose may exceed the toxicology NOAEL. Each dose will be separated by at least 1 week. The initial single dose level is the equivalent of 100-mg original formulation, the dose that produced maximum $AUC_{0-\infty}$ ($56 \mu\text{g}\cdot\text{h}/\text{mL}$) in Study CVAA. This dose level was selected because it produced the highest exposure when administered using the original formulation of LY3526318, and if the new formulation produces the maximum theoretical exposure increase of 2-fold compared to the prior study, a 2-fold exposure increase is considered safe and appropriate. Up to 2 additional single dose levels may be administered in a fasted state and these doses would be selected to maintain human $AUC_{0-\infty}$ below the lowest animal-toxicology NOAEL ($154 \mu\text{g}\cdot\text{h}/\text{mL}$, established in a 1-month monkey study).

Doses that were administered in a fasted state may also be administered in a fed state to determine if food decreases exposure when LY3526318 is administered in the new formulation. For the fed state, a standardized, high-fat meal or a light breakfast (as described in site-specific manual) will be consumed prior to dosing. Approximately 50% of the total caloric content of the high-fat meal should be from fat. Study participants should eat this meal in 30 minutes or less, and the study intervention should be administered 30 minutes after the start of the meal. In all cases, study intervention should be taken with 1 glass (approximately 240 mL) of water, and no food should be allowed for at least 4 hours post dose. Water can be allowed as desired except for 1 hour before and after drug administration.

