4.3. Justification for Dose

In a prior Phase 1 study (CVAA), there were no clinically significant adverse events at the highest doses administered: 300 mg in the SAD and 100 mg/day for 14 days in the MD. These doses were administered to females only, but there was no apparent difference in exposure or tolerability at lower doses administered to males and females. 100 mg/day was selected as the highest dose for the MD, because plasma exposure did not increase with increasing dose beyond 100 mg. In addition, when a meal was consumed 30 minutes prior to a 100 mg dose, exposure was approximately 11% of that observed when participants fasted. The new formulation being administered in the current study was developed to increase absorption and to decrease the impact of food. The current formulation could produce exposures up to 2.5 times those of the prior form for any given dose level.

The NOAEL from Good Laboratory Practice toxicology studies was established in a 1-month monkey study (Study 00926044). There were no adverse effects in monkeys administered 1000 mg/kg/day, and the mean AUC₀₋₂₄ was 154 $\mu\text{g}\cdot\text{h}/\text{mL}$. As summarized in Table 4.1, in the clinical study, CVAA, a dose of 100 mg resulted in a mean AUC_{0-inf} of 56 $\mu\text{g}\cdot\text{h}/\text{mL}$, and this is planned to be the starting dose in CVAC. The planned maximum dose of 275 mg is based on an assumption of a dose-proportional increase in exposure. The determinant of the maximum dose will be the NOAEL AUC of 154 $\mu\text{g}\cdot\text{h}/\text{mL}$. In the event that a less-than-dose-proportional increase in exposure is observed, a unit dose higher than 275 mg may be used, as long as a mean AUC of 154 $\mu\text{g}\cdot\text{h}/\text{mL}$ is not exceeded. As a practical limit, the unit dose will not be more than 1000 mg. In addition, if a dose lower than 100 mg is needed to maintain AUC < 154 $\mu\text{g}\cdot\text{h}/\text{mL}$, de-escalation is permitted. For the multiple-dose portion of the study, the dose regimen and fed/fasting will be selected with the intent not to exceed the AUC₀₋₂₄ achieved in Part A.

Table 4.1. Margin of Safety for Oral Administration of LY3526318 Based on Administered Dose and Exposure

	Dose (mg/kg)	Dose (mg/m ²)	Dose Multiple ^a	AUC ($\mu\text{g}\cdot\text{h}/\text{mL}$) ^a	Exposure Multiple ^b
Human					
Starting dose (100 mg)	1.67	61.7		56	
Maximum dose (275 mg) ^c	4.6	170		154	
Rat NOAEL^d					

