Male	1000	6000	97 ^e 35 ^f	131	2.3 ^e 0.85 ^f
Female	1000	6000	97 ^e 35 ^f	295	5.3 ^e 1.9 ^f
Monkey NOAEL^g	1000	12000	194 ^e 71 ^f	154	2.8 ^e 1 ^f

Abbreviations: AUC = area under the concentration versus time curve; AUC_{0-inf} = area under the concentration versus time curve from time zero to infinity; AUC_τ = area under the concentration versus time curve during a dosing interval; NOAEL = no-observed-adverse-effect level.

- ^a AUC for humans is AUC_{0-inf} after a single dose. AUC for rat and monkey is AUC_τ after multiple doses.
- ^b Dose multiple is the dose in animals/dose in humans based on mg/m². Exposure multiple is the calculated AUC in animals/observed or predicted AUC in humans.
- ^c The planned maximum dose of 275 mg is based on an assumption of dose-proportional increase in exposure. The determinant of the maximum dose will be the NOAEL AUC of 154 $\mu\text{g}\cdot\text{h}/\text{mL}$. In the event that a less-than-dose-proportional increase in exposure is observed, a unit dose higher than 275 mg may be used, as long as a mean AUC of 154 $\mu\text{g}\cdot\text{h}/\text{mL}$ is never exceeded. As a practical limit, the unit dose will not be more than 1000 mg.
- ^d NOAELs from the 4-week, repeat-dose toxicity study (Study # 00926043).
- ^e Based on human exposure at 100 mg using the prior formulation (Study CVAA).
- ^f Based on the highest projected exposure (NOAEL of 154 $\mu\text{g}\cdot\text{h}/\text{mL}$) at a 275 mg dose using the new formulation.
- ^g NOAEL from the 4-week, repeat-dose toxicity study (Study # 00926044; no LY3526318-related effects were noted).

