6.0 Study Design

This is a Phase 1, randomized, double-blind and placebo-controlled single ascending dose (SAD, Part A) and multiple dose (MD, Part B) study of LY3526318 in healthy participants. A maximum of 16 participants (SAD and MD cohorts, size of 8) will be enrolled.

Part A (SAD):

A single cohort of 8 healthy participants will be randomized to a sequence in which LY3526318 or placebo will be administered in a 3:1 ratio. In each dosing period, different participants will receive placebo. In this adaptive dose study, subsequent dose levels will be selected based on safety and PK. Doses will be selected to maintain geometric mean $AUC_{0-\infty}$ below the lowest no-observed-adverse-effect level (NOAEL) from animal toxicology studies (154 μ g.h/mL).

Of the 4 treatment periods planned for Part A, up to 3 single dose levels will be assessed in a fasted state (fasting at least 8 hours prior to and at least 4 hours after dosing). Up to two of these dose levels that were assessed in a fasted state may also be assessed in a fed state (a high-fat meal or a light breakfast 30 minutes prior to dosing).

Randomized to Treatment/Sequence:

Treatment	SAD Periods [N=8]				
	Sequence [n]	A1 (f asted)	A2 (f asted)	A3 (f ed)	A4 (f ed)
1 [2]		P	L2	L3	L4
2 [2]		L1	P	L3	L4
3 [2]		L1	L2	P	L4
4 [2]		L1	L2	L3	P

Single doses are L1, L2, L3, L4, P (Placebo); L = level of dose (mg);

Abbreviations: N = number of participants; n = number of participants in specific population; SAD = single ascending dose.

Following a screening period of up to 28 days, eligible participants will be confined to the clinical research unit (CRU) from Day -1 until all study assessments are completed on Day 3. All participants will return to the CRU after the last study period for a final visit on Day 10.

Part B (MD):

After a dose is identified from Part A, multiple doses of LY3526318 or placebo will be administered for up to 5 days. Eight treatment-naïve participants will be randomized to receive LY3526318 or placebo in a 3:1 ratio. Additional participants will be enrolled for a total cohort size of 8 completers. Part B will involve dosing in a f asted or f ed state (e.g., standard meal or a light breakfast as described in site-specific manual) depending on the results from Part A. The dose regimen and fed/fasting will be selected with the intent not to exceed the AUC₀₋₂₄ achieved in Part A. Part B is not designed to assess the impact of food on exposure.

Randomized to Treatment/Sequence:

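### The Part A cap of 154 µg·h/mL is set on AUC0-24 in the protocol synopsis but on AUC0-inf in Section 4.1, Table 4.1 and SAP 6.0, so the synopsis states a looser limit than the operative one

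*Protocol*

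**What the plan says.** Five places in the two documents bear on the Part A exposure limit.

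- **Protocol 1.1 (Synopsis), Part A:** "Doses will be selected to maintain geometric mean AUC_{0-24} below the lowest NOAEL from animal-toxicology studies", given as 154 µg·h/mL. The next paragraph bases escalation on safety data and "available PK data through 24 hours post dose from at least 4 participants on active drug". The synopsis rationale mentions the same limit but speaks only of human exposure, with no AUC type.
- **Protocol 4.1:** for the additional fasted dose levels, "these doses would be selected to maintain human $AUC_{0-\infty}$ below the lowest animal-toxicology NOAEL", again 154 µg·h/mL. Section 9.5 refers to 4.1 for how interim PK data support escalation and dose selection.
- **Protocol 4.3:** of the source of the limit, "There were no adverse effects in monkeys administered 1000 mg/kg/day, and the mean AUC₀₋₂₄ was 154" µg·h/mL. Of the top dose, "The planned maximum dose of 275 mg is based on an assumption of a dose-proportional increase in exposure". Table 4.1 footnote a adds: "AUC for humans is AUC_{0-inf} after a single dose"; the animal values are dosing-interval AUCs after multiple doses. The text and footnote c state the human cap as a mean AUC, without saying which AUC or which mean.
- **Protocol 6.6.1:** escalation continues until mean exposure is projected to reach the NOAEL, using PK through at least 24 hours. The AUC type is not named here.
- **SAP 6.0:** "Doses will be selected to maintain geometric mean $AUC_{0-\infty}$ below the lowest no-observed-adverse-effect level". SAP 7.1 declares no changes from the protocol, which is true against 4.1 but not against the synopsis.

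**The concern.** One number, 154, is attached to two different exposure measures. AUC0-inf exceeds AUC0-24 whenever drug remains in plasma at 24 hours, so a limit of 154 on AUC0-24 is looser whatever PK model holds. The synopsis puts that looser limit beside a 24-hour PK review, at which point AUC0-24 has been observed and AUC0-inf still has to be extrapolated. The looser measure is therefore the easier one to apply. Section 6.6.1, where the decision rule sits, does not name the measure and so does not correct a reader who starts from the synopsis.

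The threshold limits exposure in healthy volunteers, for whom the protocol anticipates no benefit, and Table 4.1 already shows an exposure multiple of 1 against the monkey at the cap. The wording can also change an answer: for some plausible results at 100 mg, the two limits disagree on whether 250 mg is allowed.

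**Working it through.** **Inputs.** Cap 154 µg·h/mL (4.1, 4.3). Mean AUC0-inf 56 µg·h/mL at 100 mg of the prior formulation (4.3). Geometric mean half-life 9.72 to 13.5 h for the prior formulation (2.2); none is given for the new one. Male rat NOAEL AUC 131 (Table 4.1). Second fasted dose 250 mg (SAP 9.2.2).

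**1. The plan's own figures.** 100 mg × 154/56 = 275 mg, as stated. Exposure multiples against the monkey: 154/56 = 2.75 (stated 2.8) and 154/154 = 1. Against the male rat: 131/56 = 2.34 (stated 2.3) and 131/154 = 0.85. All reproduce. The 56 is an AUC0-inf, so the 275 mg maximum is an AUC0-inf calculation.

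**2. What a cap of 154 on AUC0-24 would permit.** With mono-exponential decline from time zero, AUC0-24/AUC0-inf = 1 − 2^(−24/t½).

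| t½ (h) | AUC0-24/AUC0-inf | AUC0-inf when AUC0-24 = 154 | Excess over 154 | AUC0-24 when AUC0-inf = 154 |
|---|---|---|---|---|
| 9.72 | 0.819 | 154/0.819 = 187.9 | 22% | 126 |
| 13.5 | 0.708 | 154/0.708 = 217.4 | 41% | 109 |

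At 56 per 100 mg, 187.9 and 217.4 correspond to about 336 and 388 mg, against 275 mg. The exposure multiples there would be 154/187.9 = 0.82 and 154/217.4 = 0.71 for the monkey, and 131/187.9 = 0.70 and 131/217.4 = 0.60 for the male rat.

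**3. Sensitivity to the model.** For one-compartment oral absorption with k = ln 2/t½, the ratio is 1 − (ka·e^(−24k) − k·e^(−24ka))/(ka − k).

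| Assumption | AUC0-inf permitted |
|---|---|
| ka = 0.5/h | 195 (t½ 9.72 h) to 228 (13.5 h) |
| ka = 0.2/h | 213 to 252 |
| AUC0-24/AUC0-inf = 0.90 to 0.95 (marked early distribution) | 154/0.90 = 171 to 154/0.95 = 162 |

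Every case is above 154; the size depends on the model.

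**4. Where the two wordings disagree on 250 mg,** assuming dose proportionality and the ratios in step 2. Under AUC0-inf, 250 mg is allowed if 100 mg gives less than 154/2.5 = 61.6, which is 1.10 × 56. Under AUC0-24 it is allowed up to 61.6/0.819 = 75.2 or 61.6/0.708 = 87.0, which is 1.34 or 1.55 × 56.

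| AUC0-inf at 100 mg | AUC0-inf at 250 mg | AUC0-24 at 250 mg | Section 4.1 | Synopsis alone |
|---|---|---|---|---|
| 56 | 140 | 99–115 | allows | allows |
| 70 (25% above 56) | 175 | 124–143 | bars | allows |
| 112 (2-fold) | 280 | 198–229 | bars | bars |
| 140 (2.5-fold) | 350 | 248–287 | bars | bars |

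The 2-fold row is the "maximum theoretical exposure increase of 2-fold compared to the prior study" in Section 4.1; the 2.5-fold row is the upper figure in 4.3. Section 2.3 expects the new formulation at 100 mg to match or slightly exceed the prior exposure, so the disagreement begins (10% above 56) close to what is expected.

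**5. Type of mean.** The synopsis and SAP 6.0 specify the geometric mean; 4.3 and footnote c say only mean; 4.1 and footnote a name no mean. For log-normal data the arithmetic mean is √(1 + CV²) times the geometric mean: 1.12 at an assumed CV of 50% and 1.41 at 100%. The documents report high interindividual variability but give no CV.

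**The case against.** The best defence is that the protocol does say which section governs. Section 9.5 points escalation to 4.1, and Sections 2.3 and 6.1 point to 4.3, whose table uses human AUC0-inf; no cross-reference sends dose selection to the synopsis. The limits are also nested: any dose that keeps AUC0-inf below 154 keeps AUC0-24 below it too. Footnote c says the mean AUC of 154 is not to be exceeded, and every dose decision needs agreement between the investigator and the sponsor's medical monitor. All of this stands. It limits the fault to the synopsis wording and an unspecific phrase in 6.6.1. A reader might infer that the protocol leaves the measure open; read as a whole, it does not.

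A second defence is that 4.3 labels the monkey value AUC0-24, so the synopsis compares like with like. That may explain the wording, but footnote a makes the animal value a dosing-interval AUC after repeated dosing. Under linear PK, the single-dose human quantity equal to a steady-state dosing-interval AUC is AUC0-inf, as Table 4.1 uses. Linearity is an assumption: with the prior formulation, exposure stopped rising above 100 mg. Even so, the documents' own margin and the 275 mg figure rest on AUC0-inf.

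A third is that 188 to 217 needs a PK model and the prior formulation's half-life. This is correct, so the wider range belongs beside it.

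**Conclusion.** The concern holds as a minor error: the synopsis is wrong as written. It states the Part A limit on AUC0-24, while Section 4.1, Table 4.1 and SAP 6.0 use AUC0-inf. The direction needs no model. Read alone, the synopsis would permit AUC0-inf of about 188 to 217 µg·h/mL under mono-exponential decline and a half-life of 9.72 to 13.5 h, with 162 to 252 across the other cases examined.

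Two stronger readings are not supported. A reader might infer that the plan allows exposure above the NOAEL; it does not if all sections are followed. A reader might also infer that 250 mg was chosen under the looser limit. The documents do not show which measure supported that dose, and if 100 mg gave the prior 56, both limits allow it.

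**What to change.** 1. In the Part A paragraph of the synopsis, change the capped measure from AUC0-24 to AUC0-inf.
2. In Section 6.6.1, replace the general reference to mean exposure with mean AUC0-inf, projected against 154 µg·h/mL as in Section 4.1.
3. State one type of mean in the synopsis, 4.1, 4.3 with Table 4.1, 6.6.1 and SAP 6.0. The geometric mean is the looser choice and the arithmetic mean the more cautious; the sponsor should choose deliberately.

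The cost is a few words in the protocol, and in SAP 6.0 if the arithmetic mean is chosen. There is no change to design, sampling or timing. Requiring the 48-hour sample before each decision is not part of the fix, because 6.6.1 already allows PK data beyond 24 hours.

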1.2. Schema

[figure not shown]

Figure 1.1. Study diagram.

Randomized to Treatment/Sequence

Treatment	SAD Periods [N=8]			
Sequence [n]	A1	A2	A3	A4
1 [2]	P	L2	L3	L4
2 [2]	L1	P	L3	L4
3 [2]	L1	L2	P	L4
4 [2]	L1	L2	L3	P

Single doses are L1, L2, L3, L4, P (Placebo); L = level for dose (mg)

Treatment	MD [N=8]
Sequence [n]	B
5 [6]	LX
5 [2]	P

Multiple Dose (MD) is dose LX that is \leq single dose

Abbreviations: N = number of participants; n = number of participants in specific population; SAD = single ascending dose.

Figure 1.2. Study treatments for the SAD and MD cohorts.

1.3. Schedule of Activities

Table 1. Study Schedule Protocol J2D-MC-CVAC Single-Ascending Dose (SAD) – Part A

	S	Treatment Period ^a					FU	ED ^b
Visit	1	2			3	4	5	
Study Day	-28	-1 ^c	1	2	3	4	5	10 (± 1 day)
Admit to CRU ^d		X						
Discharge from CRU					X ^e			
CRU visit	X	X				X ^e	X ^e	X
Informed consent	X							
Medical history	X	X						
C-SSRS	X	X					X	X
Height	X							
Weight	X	X					X	X
Physical examination	C	D	D	D	D	D	D	D
Urine drug screen	X	X					X	X
Hematology and clinical chemistry	X		P	X			X	X
Urinalysis ^f	X	X	P	X			X	X
β -hCG pregnancy test	X	X					X	X
HIV, HCV, HBsAg	X							
Con med		X	X	X	X	X	X	X
Adverse events	X	X	X	X	X	X	X	X
Vital signs	X	X	P, 2, 4, 6 h	X	X	X	X	X
Temperature	X	X						
ECG ^g					See Table 2			
Randomization			X					
Study intervention administration ^h			X					
PK blood sample ⁱ					See Table 2			

Abbreviations: C = complete physical examination; Con med = concomitant medications; COVID-19 = coronavirus disease 2019; CRU = clinical research unit; C-SSRS= Columbia-Suicide Severity Rating Scale; D = directed physical examination; ECG = electrocardiogram; ED = early discontinuation; FU = safety follow-up; HBsAg = hepatitis B surface antigen; β -hCG = beta subunit of human chorionic gonadotropin; HCV = hepatitis C virus; HIV = human immunodeficiency virus; P = predose assessment; PK = pharmacokinetic; S = Screening; SOP = standard operating procedure.

Note: In the event that assessments are planned for the same time, assessments should be conducted in following order: ECG/vital signs/ PK sample The ECG and vital signs measurement can be obtained at least 30 minutes prior to the PK sample, which is drawn at the nominal time point.

Screening visits will be performed within 28 days before the administration of first dose.

- a The procedures for Days -1 through 5 will be repeated for up to 4 treatment periods.
- b Participants who discontinue the study prior to study completion will complete the ED visit procedures.
- c Day -1 procedures can be performed on a day prior to dosing or pre-dose on day of dosing.
- d All participants will remain in the CRU until completion of all procedures that occur that day.
- e After participants have completed the required in-house stay, the remaining activities may be completed in house or ambulatory based upon the discretion of the investigator.
- f A standard urine dipstick may be used.
- g See [Table 2](#). Triplicate 12-lead ECGs will be obtained with approximately 1 minute apart following at least 10 minutes in the supine position. Single 12-lead ECGs will be collected at the time points indicated.
- h The exact time that study intervention is administered will be recorded.
- i See [Table 2](#).

Note: All local requirements regarding COVID-19 will be followed according to local/site SOP.

Table 2. Scheduled Times^b for PK Blood Sample and ECG for Periods 1 to 4

Day ^a	Time ^b	ECG (Fasted)	ECG (Fed)	PK Sample Periods 1-4
Day -28 to -1	Screening	Single ECG		
Day 1	Predose	ECG ^c	Single ECG	X
	Dose			Dose of LY3526318
	1 h			X
	2 h	ECG ^c		X
	4 h	ECG ^c		X
	6 h	ECG ^c		X
	8 h			X
	12 h			X
Day 2	24 h	ECG ^c		X
Day 3	48 h			X
Day 4	72 h			X
Day 5	96 h			X
Follow-up visit		Single ECG	Single ECG	X
Early Discontinuation		Single ECG	Single ECG	X

Abbreviations: ECG = electrocardiogram; PK = pharmacokinetic.

a The procedures for Days -1 through 5 will be repeated for up to 4 treatment periods.

b Sampling times are given as targets to be achieved within reasonable limits. The timing of PK sample collections may be adjusted based on clinical needs. The exact sample collection dates and times must be recorded.

c Following at least 10 minutes in a supine position, triplicate ECG are collected with approximately 1 minute between measurements.

Table 3. Study Schedule Protocol J2D-MC-CVAC Multiple Dose (MD) – Part B

	S	Treatment Period								FU	ED^a	
Visit	1	2								3		
Study Day	-28	-1^b	1	2	3	4	5	6	7	8	14	
Admit to CRU^c		X										
Discharge from CRU										X ^d		
CRU visit	X	X									X	X
Informed consent	X											
Medical history	X	X										
C-SSRS	X	X									X	X
Height	X											
Weight	X	X									X	X
Physical examination	C	D	D	D	D	D	D	D	D	D	D	
Urine drug screen	X	X									X	X
Hematology and clinical chemistry	X		P	P		P	P	X	X	X	X	X
Urinalysis^e	X	X	P	X		X	X	X	X	X	X	X
β-hCG pregnancy test	X	X									X	X
HIV, HCV, HBsAg	X											
Con med		X	X	X	X	X	X	X	X	X	X	X
Adverse events	X	X	X	X	X	X	X	X	X	X	X	X
Vital signs	X	X	P and 4 h	X	X	X	X	X	X	X	X	X
Temperature	X	X										
ECG^f			See Table 4									
Randomization			X									
Study intervention administration^g			X	X	X	X	X					
PK blood sample^h			See Table 4									

Abbreviations: C = complete physical examination; Con med = concomitant medications; COVID-19 = coronavirus disease 2019; CRU = clinical research unit; C-SSRS = Columbia-Suicide Severity Rating Scale; D = directed physical examination; ECG = electrocardiogram; ED = early discontinuation; FU = safety follow-up; HBsAg = hepatitis B surface antigen; β-hCG = beta subunit of human chorionic gonadotropin; HCV = hepatitis C virus; HIV = human immunodeficiency virus; P = predose assessment; PK = pharmacokinetic; S = Screening; SOP = standard operating procedure.

^a Participants who discontinue the study prior to study completion will be expected to complete the ED visit procedures.

- b Day -1 procedures can be performed on a day prior to dosing or predose on day of dosing.
- c Participants will be confined to the CRU from Day -1 until all study assessments are completed 72 hours after the last dose
- d After participants have completed the required in-house stay, the remaining activities may be completed in house or ambulatory based upon the discretion of the investigator.
- e A standard urine dipstick may be used.
- f A single 12-lead ECG will be obtained in the supine position after at least 10 minutes rest.
- g The exact time study intervention is administered will be recorded.
- h See [Table 4](#) Part B Scheduled Times for PK Blood Samples.

Note: Screening visits will be performed within 28 days before the administration of first dose.

Note: In the event that assessments are planned for the same time, assessments should be conducted in following order: ECG/vital signs/PK sample. The ECG and vital signs measurement can be obtained at least 30 minutes prior to the PK sample, which is drawn at the nominal time point.

Note: All local requirements regarding COVID-19 will be followed according to local/site SOP.

Table 4. Part B Scheduled Times for PK Blood Samples and Single 12-lead ECGs

Day	Time ^a	PK Collections ^b	ECG (fasted)	ECG (fed)
Day 1	Predose	X	X	X
	Dose	Dose of LY3526318		
	1 h	X		
	2 h	X	X	
	4 h	X	X	X
	6 h	X	X	X
	8 h	X		
	12 h	X		
Day 2	Predose (24 hours after the preceding dose)	X	X	X
	Dose	Dose of LY3526318		
Day 3	Predose (24 hours after the preceding dose)	X		
	Dose	Dose of LY3526318		
Day 4	Predose (24 hours after the preceding dose)	X		
	Dose	Dose of LY3526318		
Day 5	Predose (24 hours after the preceding dose)	X	X	X
	Dose	Dose of LY3526318		
	1 h	X		
	2 h	X	X	
	4 h	X	X	X
	6 h	X	X	X
	8 h	X		
	12 h	X		
Day 6	+24 h (24 hours after the preceding dose)	X	X	X
Day 7	+ 48 h	X		
Day 8	+72 h	X		
Follow-Up		X		
Early Discontinuation		X	X	X

Abbreviations: ECG = electrocardiogram; PK = pharmacokinetic.

a Sampling times are given as targets to be achieved within reasonable limits.

b The timing of PK sample collections may be adjusted based on clinical needs. The exact sample collection dates and times must be recorded.

2. Introduction

